### FAIM

The FAIM is a self-report instrument intended to reflect the perception of food allergy severity and related risk as evaluated by the subject using a different form by age group (8-12 years and 13-17 years) ([van der Velde, 2010](#)). Evaluations are also done by the parent/caregiver using a different form by age group (4-12 years and 13-17 years). The instrument consists of 6 questions (4 expectation of outcome questions and 2 disease severity questions). The parent/caregiver versions include questions related to perception of disease severity and expectation of allergen exposure outcome. The parent/caregiver form includes 8 questions for subjects aged 4-12 years and 4 questions for subjects aged 13 to 17 years. Each question contains response options from 0 (limited severity perception) to 6 (greatest severity perception). The FAIM is scored on a 7-point scale from 1 to 7, and the total FAIM score is calculated as the arithmetic average of all nonmissing items.

Descriptive statistics for each item and the total scores along with their changes from baseline will be tabulated. Data will be summarized separately by age group and responder (subject or parent/caregiver).

Listing of the raw scores as recorded in the case report form will be provided, sorted by treatment group and subject ID.

### **9.8.13 Assessment of GI Symptoms by Pediatric Eosinophilic Esophagitis Symptom Scores**

Subjects who discontinue treatment due wholly or in part to GI adverse events will be instructed to complete the Pediatric Eosinophilic Esophagitis Symptom Scores (PEESS v2.0) questionnaire ([Martin, 2015](#); [Franciosi, 2011](#)) monthly for 6 months.

The PEESS questionnaire is composed of 20 items investigating the frequency and severity of eosinophilic esophagitis (EoE) symptoms in the last month. The total score consists of all 20 items. The frequency of symptoms is assessed by items 1, 3, 5, 7, 9, 11, 13, 15, 17, 19, and 20, where each item is scored as: 0 = Never, 1 = Almost never, 2 = Sometimes, 3 = Often, 4 = Almost always. The severity of symptoms is assessed by items 2, 4, 6, 8, 10, 12, 14, 16, and 18, where each item is scored as 0 = Not bad at all, 1 = A little bad, 2 = Kind of bad, 3 = Bad, 4 = Very bad. Each item score is transformed to 0-100 as follows: 0 = 0, 1 = 25, 2 = 50, 3 = 75, 4 = 100.

The total, frequency total, and severity total scores are computed as the sum of the items divided by the number of items answered. If more than 50% of the items for the calculation of a score are missing, the score will not be calculated.

Summary statistics for frequency of symptoms, severity of symptoms, and the total score will be summarized for the safety population by age group (4-11 years on parent report only, 8-11 years on children and teen report only, 8-17 years on children and teen report only, 12-17 years, 4-17 years on parent report only), treatment group (AR101, placebo) and time point. PEESS results including the frequency total, severity total, and total scores will be listed.

#### **9.8.14 Physical Examination**

Physical examination results will be listed by age group, treatment group, subject, and visit.

#### **9.8.15 Peak Expiratory Flow Rate and Spirometry**

Peak expiratory flow rate (PEFR) assessments are performed throughout the study. Three attempts of PEFR are performed and the best (highest) value flagged in data listings. Only the best PEFR value will be summarized.

Spirometry may be performed at screening. Three attempts of FEV1 are performed. Spirometry results are listed but are not summarized.

Observed values for PEFR as well as changes from baseline will be summarized for the safety population by age group (4-11 years, 12-17 years, 4-17 years), treatment group (AR101, placebo), and at each applicable visit. Results will be listed by age group, treatment group, subject, and visit.

#### **9.8.16 Pregnancy Test Results**

Pregnancy test results will be listed by age group, treatment group, subject, and visit.

#### **9.8.17 Laboratory Assessments**

Laboratory data consists of hematology tests. Laboratory data are collected at baseline and the 300 mg study site visit.

Observed values for each laboratory parameter as well as changes from baseline will be summarized for the safety population by age group (4-11 years, 12-17 years, 4-17 years), treatment group (AR101, placebo), and at each applicable visit. For each laboratory parameter, a shift table based on the normal range (low, normal, and high) will be provided to summarize the baseline result versus the worst postbaseline result.

Results will be listed by age group, treatment group, subject, and visit.

#### **9.8.18 Vital Signs**

Vital signs (body temperature, heart rate, systolic/diastolic blood pressure) will be listed by subject and visit. Observed values and change from baseline will be summarized for the

safety population by age group (4-11 years, 12-17 years, 4-17 years), treatment group (AR101, placebo), and at each scheduled visit and time point. At initial escalation, up-dosing, and 300 mg QD visits, vital signs are taken predose and within 15 to 30 minutes after each dose is given. Vital signs are also taken at Exit and Early Discontinuation visits.

Additional vital signs measurements taken due to extension of the observation period will not be included in the summaries. All results will be listed by age group, treatment group, subject, visit, and time point.

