Subjects may drink fluids and eat foods to which they are not allergic during the day of the initial day escalation procedure while they are being given the desensitization doses. At a minimum, subjects must be observed for 1.5 hours after completion of dose escalation, with vital sign measurements and assessment for signs and symptoms of allergic reaction performed every 30 minutes. Any signs or symptoms of allergic reaction will be recorded in the case report form (CRF) on the appropriate Dosing Symptom/AE form.

If Day 1 dose escalation is completed with no symptoms detected after 1.5 hours of post-dose observation, the subject will be able to leave the CRC. If the subject exhibited mild symptoms,

the duration of the observation period should be a minimum of 1 hour after resolution of the symptoms. For moderate symptoms, the observation period should be extended to a minimum of 2 hours after resolution of the symptoms. And for severe symptoms, the subject should be observed for a minimum of 3 hours after resolution of the symptoms, either at the CRC or an emergency facility, as appropriate.

Any subject deemed to have severe symptoms that include hypoxia, hypotension, or change in mental status, stage 3 anaphylaxis defined in [Appendix 4](#), or who receives intensive therapy (to be determined by the Investigator, but may include such interventions as IV epinephrine, intubation, or admission to an intensive care unit) for an allergic reaction at any time should be discussed with the Medical Monitor and discontinued from the study.

If dose-limiting symptoms occur at or before the 3 mg single dose, there will be no further dosing of IP, and the subject will be classified as an escalation failure and a non-responder for the purpose of primary and key secondary analyses. The subject will be asked to return to the CRC 14 days following the last dose of IP to undergo an Early Discontinuation Visit (Section [6.3.6](#)). AEs will be evaluated from the onset until the event is resolved or medically stable, or until 30 days after the Early Discontinuation Visit, whichever comes first.

If no dose-limiting symptoms occur during Day 1 dose escalation, or if dose-limiting symptoms occur only with the 6 mg single dose, the subject is to return to the CRC on Day 2 to confirm the tolerability of a single 3 mg dose of IP.

6.3.2 Initial Escalation: Day 2

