Appendix 4: Criteria for Suspected Diagnosis, and Severity Grading, of Anaphylaxis

Criteria for Suspected Diagnosis

Anaphylaxis is likely when any 1 of the 3 following sets of criteria is fulfilled:

1. Acute onset of an illness (minutes to hours) with involvement of:
 - Skin/mucosal tissue (eg, *generalized* hives, itch or flush, swollen lips/tongue/uvula) *AND*
 - Airway compromise (eg, dyspnea, stridor, wheeze/ bronchospasm, hypoxia, reduced PEFR) *AND/OR*
 - Reduced BP or associated symptoms (eg, hypotonia, syncope, incontinence)
2. Two or more of the following that occur rapidly after exposure to the allergen (minutes to hours):
 - Skin/mucosal tissue (eg, *generalized* hives, itch/flush, swollen lips/tongue/uvula)
 - Airway compromise (eg, dyspnea, stridor, wheeze/bronchospasm, hypoxia, reduced PEFR)
 - Reduced BP or associated symptoms (eg, hypotonia, syncope, incontinence)
 - *Persistent* GI symptoms (eg, nausea, vomiting, crampy abdominal pain)
3. Reduced BP after exposure to the allergen (minutes to hours):
 - Infants and children: low systolic BP (age-specific) or > 30% drop in systolic BP*
 - Adults: systolic BP < 90 mm Hg or > 30% drop from their baseline

* *Low systolic BP for children is defined as < 70 mmHg from 1 month to 1 year; less than (70 mmHg + [2 x age]) from 1 to 10 years; and < 90 mmHg from age 11 to 17 years.*

Note: Isolated skin or mucosal lesions following the ingestion of a food constitute a food-induced allergic reaction.

Criteria for Anaphylaxis Severity Grading

Staging System of Severity of Anaphylaxis	
Stage	Defined by
1. Mild (skin and subcutaneous tissues, GI, and/or mild respiratory)	Flushing, urticaria, periorbital, or facial angioedema; mild dyspnea, wheeze, or upper respiratory symptoms; mild abdominal pain and/or emesis
2. Moderate (mild symptoms + features suggesting moderate respiratory, cardiovascular or GI symptoms)	Marked dysphagia, hoarseness, and/or stridor; shortness of breath, wheezing and retractions; crampy abdominal pain, recurrent vomiting, and/or diarrhea; and/or mild dizziness
3. Severe (hypoxia, hypotension, or neurological compromise)	Cyanosis or SpO ₂ ≤ 92% at any stage; hypotension; confusion; collapse; loss of consciousness; or incontinence

Criteria for diagnosis and for severity grading adapted from [Muraro et al, 2007](#), and [Muraro et al, 2014](#).

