## 7.2 Programming Conventions

Unless stated otherwise, the term “descriptive statistics” refers to the number of subjects (n), mean, median, standard deviation, minimum, and maximum for continuous variables and frequencies and percentages for categorical variables.

Unless specified otherwise, the denominator for percentages for categorical data will be based on the number of subjects or observations with nonmissing data appropriate for summary purposes. The denominator for percentages for incidence data (such as adverse events) will be based on the number of subjects in the analysis population “at risk”.

Minimum and maximum values will be presented at the precision of the original value, means, medians will be rounded to 1 decimal place greater than the precision of the original value, standard deviations and standard errors will be rounded to 2 decimal places greater than the precision of the original value. Percentages will be rounded to 1 decimal place. Percentages that round down to 0 or up to 100% will be displayed as “< 0.1%” and “> 99.9%”, respectively.

All summary tables will be presented by treatment group displayed as AR101 and placebo. For disposition, demographic, and other summaries of baseline and history data, a total column for both treatment groups combined will be included.

All relevant data collected in the database will be included in data listings and sorted by treatment group, subject number, and visit and time point as appropriate. The treatment group will be displayed by AR101 then placebo.

Unscheduled visits will be listed but not included in by-visit summaries. Results from unscheduled visits may be used as baseline values and for other derivations not tied to visit names (for example, unscheduled visits are included in the determination of worst postbaseline values for laboratory shift tables).

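### Blood-pressure falls seen only in extended-observation or unscheduled readings are listed but never counted by arm, because vital signs have no worst-value or threshold table

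*SAP*

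**What the plan says.** SAP 9.8.18 (Vital Signs) summarises observed values and change from baseline at each scheduled visit and time point. For dosing visits it notes that "vital signs are taken predose and within 15 to 30 minutes after each dose is given". It then states: "Additional vital signs measurements taken due to extension of the observation period will not be included in the summaries". Nothing is discarded: "All results will be listed by age group, treatment group, subject, visit, and time point".

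Four other provisions bear on this.

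- **Unscheduled visits.** SAP 7.2: "Unscheduled visits will be listed but not included in by-visit summaries". The same paragraph allows unscheduled results in derivations not tied to a visit name, and gives worst postbaseline laboratory values as the example.
- **Baseline.** SAP 7.1 defines it as the last nonmissing value before the first dose of randomised treatment.
- **Worst values.** SAP 9.8.17 gives hematology a shift table "to summarize the baseline result versus the worst postbaseline result". SAP 9.8.18 has no equivalent.
- **What extends observation.** Protocol 6.3.1 to 6.3.3 set a routine minimum of 1.5 hours after dosing and a longer stay when symptoms occur. Protocol 6.3.1 says, for example: "For moderate symptoms, the observation period should be extended to a minimum of 2 hours after resolution of the symptoms". The corresponding minimum is 1 hour after resolution for mild symptoms and 3 hours for severe symptoms. Protocol 6.5.4 lists a longer interval between Day 1 doses among the responses to symptoms.

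Protocol Appendix 4 makes reduced blood pressure after exposure sufficient by itself to suspect anaphylaxis. For children the criterion is "low systolic BP (age-specific) or > 30% drop in systolic BP".

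**The concern.** Whether a reading enters the summary depends partly on whether the child reacted. Readings added because of symptoms go to listings only. So do readings from unscheduled visits, some of which are made to assess tolerability, reduce a dose or manage an adverse event.

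The planned statistics also do not measure an acute fall. On Day 1 the SAP baseline and that day's predose value normally coincide. From Day 2 onward they do not, and by late up-dosing they are months apart, so change from baseline is no longer the change produced by that visit's dose.

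The primary objective is safety and tolerability, and Protocol 5.10 names a drop in blood pressure with severe anaphylaxis, and a sudden rise after epinephrine, as hazards. The protocol supplies a numeric criterion and the data are collected, yet no planned table counts, by arm, the children whose measured pressure met it.

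**Working it through.** The documents give no vital-sign figure for this point, so there is nothing to reproduce. The check traces each kind of reading, then asks what the planned statistics could show.

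**1. Where each reading goes**

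| Reading | Protocol source | Handling in the SAP |
|---|---|---|
| Predose; 15 to 30 minutes post-dose | 6.3.1 to 6.3.3 | Summarised, with minimum and maximum (7.2, 9.8.18) |
| Routine, every 30 minutes to 1.5 hours | 6.3.1 to 6.3.3 | Unclear: 9.8.18 does not name these as time points |
| Later, because of symptoms | 6.3.1 to 6.3.3 | Listing only |
| Unscheduled visit | 6.3.3, 6.4 | Listing only |

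**2. How many readings the extension holds**

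Let symptoms resolve t minutes after the dose. The minimum stay is then t + 60 (mild), t + 120 (moderate) or t + 180 (severe) minutes. The part beyond the routine 90 minutes is max(0, t − 30), t + 30 or t + 90. Counting one reading every 30 minutes:

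- t = 30: 0, 60 or 120 minutes, so 0, 2 or 4 readings;
- t = 90: 60, 120 or 180 minutes, so 2, 4 or 6 readings.

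A moderate or severe reaction therefore always produces an extension; a mild one does so only if it resolves after 30 minutes.

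**3. What a mean can show**

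AR101 arm: 500 × 2/3 ≈ 333 subjects. Shift in the mean = 0.30 × systolic pressure × k / 333, for k children with a 30% fall. Systolic pressure is not given in the documents; 95 to 115 mmHg is an assumption.

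- k = 1: 0.30 × 95 / 333 = 0.09 to 0.30 × 115 / 333 = 0.10 mmHg
- k = 3: 0.26 to 0.31 mmHg
- k = 10: 0.86 to 1.04 mmHg

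Even if every reading were included, a by-visit mean would hardly move.

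**4. What the planned minimum can show**

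Appendix 4 sets the low limit for ages 1 to 10 at 70 + 2 × age: 78 mmHg at age 4, 84 at 7, 86 at 8 and 90 at 10. In the 4 to 11 age group, a table minimum of 85 mmHg would be low for a child of 8 and not low for a child of 7. The minimum gives no count and no percent fall, and it covers summarised time points only.

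**5. What a count would show**

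With 0 of 333 AR101 subjects meeting the criterion, the one-sided 95% upper bound is 1 − 0.05^(1/333) = 0.9%. The chance of at least one case is 1 − (1 − p)^333: 63%, 96% and over 99.9% for assumed true rates p of 0.3%, 1% and 3%. Either result would be informative.

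**The case against.** The strongest reply is that recognised falls are already tabulated.

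- Protocol 7.3.1 makes any change the investigator considers clinically significant an adverse event, and Protocol 7.1 treats in-clinic allergic symptoms as adverse events.
- SAP 9.8.1 tabulates events of grade 3 or higher and events starting within 90 minutes of dosing at the site.
- SAP 9.8.3 tabulates anaphylaxis by maximum severity and individual symptom; Appendix 4 places hypotension in the severe stage.
- SAP 9.8.6 gives maximum in-clinic symptom severity by dose level.

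This stands, and it rules out one inference a reader might draw: that blood-pressure falls vanish from the safety summary. Falls at scheduled time points also remain, with minimum and maximum. What these tables do not provide is a count of measured values against Appendix 4. They rest on the investigator judging the change significant or reporting a symptom or anaphylaxis.

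A reader might also infer that the exclusion pulls the AR101 mean toward placebo. The documents do not support this. Reacting children keep their scheduled readings. The extension minimums run from symptom resolution, so many excluded readings may be recovery values, some after epinephrine, which Protocol 5.10 says can raise pressure sharply. Neither the direction nor the size of any shift is established.

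Nor are all unscheduled visits reaction-driven: Protocol 6.4 schedules them every 4 weeks or sooner for children waiting for follow-on protocols. Finally, vital signs are not a named endpoint in SAP 4 and the study is descriptive, which limits the weight of the point.

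**Conclusion.** The point holds in a limited form. Blood-pressure falls that appear only in extended-observation or unscheduled readings reach the listings but no by-arm count, unless the investigator recorded them as an adverse event or anaphylaxis symptom. One of the two exclusions, that of extended-observation readings, depends on the outcome under study. The change statistic does not measure a same-visit fall after Day 1, and no worst-value or threshold summary fills the gap.

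The number of children affected cannot be derived from the documents. The mean shifts above rest on an assumed systolic pressure, and the detection probabilities on assumed event rates. This is an inexpensive improvement to the safety reporting; it does not undermine the primary endpoint.

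**What to change.** Keep the by-visit summaries and add one table to SAP 9.8.18, by treatment group, age group and study period. Use all in-clinic post-dose readings, including those from extended observation and unscheduled visits. Show per subject:

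- the lowest post-dose systolic pressure;
- the largest percent fall from the same visit's predose value;
- whether the Appendix 4 reduced-pressure criterion was met, reported as n (%) of subjects.

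State the reference for the percent fall in the table, since the children's line in Appendix 4 does not name one. State also whether the routine 30-minute readings count as scheduled time points.

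Footnote three limits: reacting children have more readings, so their worst values are somewhat more extreme; some readings follow rescue medication; and the count is of measured values, so it may differ from the diagnosed anaphylaxis in SAP 9.8.3.

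The cost is SAP wording and one table from data already collected and listed. Using unscheduled readings agrees with the allowance in SAP 7.2. No study procedure changes.

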## 10 PRE-DATABASE LOCK BLINDED DATA REVIEWS

Major data queries that have or may have bearing on the safety aspects of the study will be resolved prior to unblinding individual subjects. These include:

- Fulfillment of inclusion/exclusion criteria
- Accidental peanut exposures that resulted in serious adverse events or adverse events
- Severity and relationship to investigational product of serious adverse events and adverse events

The purpose of the predatabase lock blinded data review is for identification of major and minor protocol deviations.

Only ARC007 project team members who are blinded to study treatment assignments (ie, medical monitor, statistician, data manager, sponsor clinical project staff) will be involved in the data reviews.

